7.0 Treatment Plan

- 7.1 Eligible patients will be randomized in equal numbers to each treatment arm using CORe. Randomization will be stratified using the following factors:7.1.1 RPA class (III or IV vs. V)
 - 7.1.2 Mini Mental Status Examination score (21-26 vs. 27-30)
 - 7.1.3 Age (less than 65 vs. 65 or older)
- 7.2 Following randomization, insurance pre-authorization will be obtained for the specified treatment modality. If a patient's insurance will not cover payment for the assigned treatment arm, that patient will be removed from the study and will be treated off protocol.
- 7.3 Radiation target definition for glioblastoma as follows. GTV defined as tumor cavity and any T1 tumor enhancement. CTV will include GTV + 2 cm margin customized to include FLAIR enhancement (if thought by the radiation oncologist to be tumor) and exclude bone, fascia, and other anatomical barriers. PTV-50 will include CTV + 3-5 mm and will be treated to 50 Gy in 30 fractions. PTV-60 boost volume will include GTV + 3-5 mm and will be treated to 60 Gy in 30 fractions.
- 7.4 For patients randomized to IMRT, treatment will be planned using Pinnacle software system. Planning will be based on non contrast CT images obtained at time of simulation in addition to MRI scan. Treatment will be delivered using linear accelerator. Fractionated radiation will be delivered daily M-F with weekends off for all patients. IMRT plans use a configuration of five to seven isocentric 6-MV photon beams delivered in a step-and-shoot technique. For inverse planning specified dose constraints are given to organs at risk including the brainstem, spinal cord, optic chiasm, optic nerves, and cochlea.

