9.0 Evaluation During Study

- 9.1 A history and physical exam will be performed at two month intervals for a total of 24 months of follow up after the completion of the assigned treatment (±30 days). Note the first evaluation after radiotherapy will frequently be performed approximately 4 weeks after completion of radiotherapy and then the study will continue with history and physical exam at 2 month intervals.
- 9.2 Neuropsychological testing will be performed at each follow up visit, up to two years post radiation treatment. Reasonable effort will be made to complete this testing prior to patients meeting with their physicians and receiving information about the status of their disease.
- 9.3 Routine MR imaging of the brain performed with and without contrast will be obtained at each follow up visit at 2 month intervals (±30 days) until recurrence or up to two years post radiation treatment. Note the first evaluation after radiotherapy will frequently be performed approximately 4 weeks after completion of radiotherapy and then the study would continue with follow-up imaging at 2 month intervals. These post-treatment scans will be analyzed and compared to baseline scans for identification of regions demonstrating changes in contrast enhancement including size, heterogeneity and rim thickness. Qualitative estimation of associated T2-FLAIR changes will also be evaluated. Early stages of malignant gliomas have demonstrated decreased water diffusion. Routinely obtained diffusion weighted images and reconstructed ADC maps will be analyzed to see if there is a difference between pre- and various post-treatment scans. Based on contrast enhancing imaging features, manually selected regions of interest on ADC maps will be

quantitatively analyzed, normalized to contralateral unaffected brain parenchyma and compared on serial scans. Similarly DTI maps and cognitive functions will be correlated.

- 9.4 Medication usage (specifically steroid dose, narcotic pain medications, antiepileptic agents, psychostimulants) will be recorded. Steroid doses will be adjusted based on clinical and radiographic criteria.
- 9.5 Requirements for more frequent evaluation will be documented. Data on unscheduled follow-ups will also be documented.

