10.2.1.3 Progressive Disease (PD): Defined as any of the following 1) \geq 25% increase in the sum of the products of perpendicular diameters of enhancing lesions compared with the smallest tumor measurement obtained either at baseline (if no decrease) or best response, on stable or increasing dose of corticosteroids; 2) significant increase in T2/FLAIR nonenhancing lesion on stable or increasing doses of corticosteroids compared with baseline or best response not caused by comorbid events (i.e. radiation therapy. demvelination, ischemic injury postoperative changes); 3) any new lesion; 4) clear clinical deterioration not attributable to other causes apart from tumor (i.e. seizures, medication adverse effects, complications of therapy, cerebrovascular events, infection, or decrease in corticosteroid dose); 5) failure to return for evaluation due to death or deteriorating condition; 6) clear progression of non-measurable disease.

When making the diagnosis of progressive disease it is import to recognize the possibility of pseudo-progression, especially if the patient is clinically stable. In those situations, treatment should continue and status of local control should be evaluated with a repeat interval scan. If the subsequent scan confirms progression then the date of progression should be backdated to the original scan suggesting progression.

- 10.2.1.4 Stable Disease (SD): Requires all of the following 1) does not qualify for complete response, partial response, or progression; 2) stable FLAIR/T2 lesions on corticosteroid dose no greater than at baseline; 3) clinical status stable.
- 10.2.1.5 For local control, PD is considered local failure, or stable disease with deterioration of the neurological examination with a grade III or worse toxicity on the CTCAE v.4.0 scale (see Appendix). All others (CR, PR, asymptomatic SD) are deemed success.
- 10.2.2 Overall survival will be measured from registration until death. After 2 years of follow-up event monitoring will be used.
 - 10.2.2.1 Patients with unknown vital status will be censored at the date of last visit or MRI scan.
- 10.2.3 Quality of life will be measured at each two month interval follow up visit out to two years using the EORTC QLQ C30/BN20 and the MD Anderson Symptom Inventory Brain Tumor (MDASI-BT).

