12.0 Statistical Considerations

- 12.1 Randomization procedure: A stratified block randomization procedure will be used. Randomization will be performed using CORe. The randomization strata are as defined above in section 7.0, and the block size will be 6. Patients who withdraw from the study after randomization, but prior to receiving treatment will be considered a cancel and replaced.
- 12.2 Sample size: With IMRT the cognitive function failure rate at 4 months is 45%, based off of comparative analyses of the cognitive failure rate of RTOG 0614 and compared to the cognitive impairment seen on RTOG 0525; we hope to demonstrate that IMPT can achieve a cognitive function failure rate at 4 months of only 30%. We assume the time to cognitive failure in each treatment arm follows an exponential distribution. A cognitive failure rate of 45% at 4 months then implies a median time to cognitive failure of 4.6 months, while a cognitive failure rate of 30% at 4 months implies a median time to cognitive failure to cognitive failure of 7.8 months.

We will use a 1-sided significance level of 0.20 as suggested by Rubinstein et al. [51]for phase II screening trials. We expect to enroll 2 patients per month, and we will randomize 60 evaluable patients (30 to each treatment arm). We will have 80% power to detect an improvement in cognitive failure at 4 months from 45% in the IMRT arm to 30% in the IMPT arm. We expect to observe 43 events, and the analysis will be performed once we have observed these events. We define evaluable patients as those who have received the assigned treatment *and* completed baseline and at least one follow-up neurocognitive testing. We expect we will need an over accrual of 33% to account for those patients not evaluable. Therefore the target total enrollment sample size is 90 patients to accrue a total of 60 evaluable patients. We expect to observe 43 events, and we expect the trial to take 41 months to observe these events.

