- 12.3 Primary Analysis: The analysis will be performed on the intention-to-treat principle. Considering those patients who are not evaluable as treatment failures. We will use the methods of Gooley et al. [52]to estimate the cumulative incidence of cognitive failure in each treatment arm, considering progressive disease and death before cognitive failure as competing events. We will estimate the cumulative incidence of cognitive failure at 4 months with 95% confidence intervals. We will use the methods of Fine and Gray [53]to test for a difference between treatment arms with respect to the cumulative incidence of cognitive failure, considering progressive disease and death before and death before and death before cognitive failure as competing events. We will use the methods of Fine and Gray [53]to test for a difference between treatment arms with respect to the cumulative incidence of cognitive failure, considering progressive disease and death before cognitive failure as competing events. Our model will include treatment arm and the stratification factors used at randomization.
- 12.4 Secondary Analysis:

We will repeat the primary analysis on only those patients considered evaluable. All the secondary analyses described below will be performed using all patients as well as using only evaluable patients. We will estimate the cumulative incidence of local failure using the methods of Gooley et al. considering death as a competing event. We will model the time to local failure using the methods of Fine and Gray to test for differences between treatment arms, considering death as a competing event. Our model will include treatment arm and the stratification factors used at randomization, as well as selected dosimetric parameters. We will similarly analyze time to distant failure.

We will use the product limit estimator of Kaplan and Meier [54] to estimate overall survival stratified by treatment arm. We will also use Cox proportional hazards regression [55] to model overall survival as a function of treatment arm and the stratification factors used at randomization.

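### The evaluable-only repeat of overall survival counts time from registration in patients who must have lived to a follow-up cognitive test, so absolute survival in that set is inflated

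*Combined protocol and SAP*

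**What the plan says.** Section 12.4 introduces its secondary analyses by saying that "All the secondary analyses described below will be performed using all patients as well as using only evaluable patients". The time-to-event analyses follow that sentence:

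- Overall survival: Kaplan-Meier estimates by arm, and "We will also use Cox proportional hazards regression [55] to model overall survival as a function of treatment arm" and the stratification factors.
- Local failure: "We will model the time to local failure using the methods of Fine and Gray to test for differences between treatment arms", with death as a competing event.
- Distant failure: "We will similarly analyze time to distant failure".

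Section 12.2 counts a patient as evaluable if he or she received the allocated treatment and "completed baseline and at least one follow-up neurocognitive testing". Section 10.2.2 sets the survival clock: "Overall survival will be measured from registration until death". Neither 12.4 nor 10.2 mentions a landmark or delayed entry, and no time origin is given for local or distant failure.

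The schedule determines how late the first follow-up test falls. Under 7.3 the boost volume "will be treated to 60 Gy in 30 fractions", and 7.4 and 7.5 restrict treatment to weekdays. Section 9.1 notes that "the first evaluation after radiotherapy will frequently be performed approximately 4 weeks after completion of radiotherapy"; otherwise visits are two months apart with a 30-day window. Section 9.2 places cognitive testing at each of these visits.

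**The concern.** Membership of the evaluable set is decided after randomization, and one condition can be met only by being alive and tested some months later. If the survival clock nevertheless starts at registration, every patient in the set is credited with an interval in which death was impossible. That is immortal time, and it raises the survival curve in each arm whatever the treatments do.

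The practical risk lies in how the result is read. Section 12.4 plans both versions without saying which one governs for survival or failure, and does not mark the evaluable version as supportive. The inflated median or 2-year figure could then be quoted or set beside historical survival. A second question is whether the comparison of arms is distorted as well.

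**Working it through.** **The plan's own figures.** The documents give no survival figure for evaluable patients, so there is none to reproduce on this point. The design figures in 12.2 do reproduce. The hazard ratio is ln(0.70)/ln(0.55) = 0.597. Schoenfeld's formula at one-sided 0.20 and 80% power gives 4(0.842 + 0.842)²/(ln 0.597)² ≈ 42.5, hence 43 events. Enrollment is 60/(1 − 0.33) ≈ 90. These concern cognitive failure, not survival.

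**Length of the guaranteed survival, L.** Thirty weekday fractions take 30/5 = 6 weeks, about 1.4 months. The first visit comes about 4 weeks (0.9 months) after radiotherapy, or at 2 months ± 30 days (1 to 3 months). The sum is roughly 2.3 to 4.4 months. Allowing a few days between registration and the first fraction, I use 2.5 to 4.5 months. A longer delay before treatment, or a missed first test, adds to L.

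**Effect on absolute survival.** The input is the 2-year survival of 27.2% with radiotherapy and temozolomide in section 4.0. The assumption is exponential survival.

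- Hazard: λ = −ln(0.272)/24 = 0.0542 per month; median = ln 2/λ = 12.8 months.
- Share dying before the test: 1 − exp(−λL).
- 2-year survival among those alive at L: 0.272/exp(−λL).
- Median from registration among those alive at L: 12.8 + L.

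| L (months) | Die before L | Of 90 enrolled | Median (months) | 2-year survival |
|---|---|---|---|---|
| none | – | – | 12.8 | 27.2% |
| 2.5 | 12.7% | 11 | 15.3 | 31.2% |
| 3 | 15.0% | 14 | 15.8 | 32.0% |
| 4 | 19.5% | 18 | 16.8 | 33.8% |
| 4.5 | 21.7% | 20 | 17.3 | 34.7% |

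The direction does not need the exponential curve: dividing by any probability below 1 raises the estimate. The size does depend on early mortality. If only 5% or 10% died before the test, the figures would be 0.272/0.95 = 28.6% or 0.272/0.90 = 30.2%.

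**Effect on the hazard ratio.** The table gives large-sample Cox estimates (IMPT versus IMRT) under the same exponential model, censored at 24 months.

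| True HR | First test, IMRT / IMPT (months) | All patients | Evaluable, from registration | Evaluable, delayed entry |
|---|---|---|---|---|
| 1.00 | 3 / 3 | 1.00 | 1.00 | 1.00 |
| 0.80 | 3 / 3 | 0.80 | 0.80 | 0.80 |
| 0.60 | 3 / 3 | 0.60 | 0.60 | 0.60 |
| 1.00 | 2.5 / 3.5 | 1.00 | 0.924 | 1.00 |
| 1.00 | 3.5 / 2.5 | 1.00 | 1.082 | 1.00 |
| 1.00 | 2.5 / 4 | 1.00 | 0.889 | 1.00 |
| 1.00 | 4 / 2.5 | 1.00 | 1.125 | 1.00 |

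With equal timing nothing happens to the ratio. The unequal timings are hypothetical; the documents do not predict them.

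**Local and distant failure.** Section 9.2 continues cognitive testing for two years, and only MRI stops at recurrence (9.3), so progression alone does not make a patient non-evaluable. MRI and testing share visits, so failures found at or after the first completed test remain in the set. Two things drop out: early deaths, which are the competing event, and progression recorded under 10.2.1.3 because death or decline kept the patient from returning. Section 10.2.1.5 counts progression as local failure. Losing competing deaths pushes estimated failure incidence up and losing failures pushes it down, so the net direction cannot be fixed from the documents.

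**The case against.** The strongest reply is that the sound analysis is already planned, in the same sentence. The evaluable-only curve duplicates a secondary endpoint; sample size and analysis timing rest on 43 cognitive events, and no success criterion uses this curve. That stands, and it limits the weight of the point. It does not remove it, because 12.4 leaves both versions on an equal footing.

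A reader might go further and infer any of the following, which the documents do not support:

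- **That the survival comparison between arms is biased.** Both arms have 30 weekday fractions and one follow-up schedule, and with equal timing the hazard ratio is unchanged. Section 7.2 removes patients whose insurer declines the assigned arm, and 5.1 acknowledges that IMPT costs more, so unequal receipt of treatment is conceivable. No rates are given, however, and such removals could also affect the all-patient set; that is selection, not immortal time.
- **That the expected 33% non-evaluable share measures the problem.** It pools patients not given the assigned treatment, those missing a baseline or follow-up test, and deaths, and the plan does not split it.
- **That the inflation is larger.** Guaranteed survival of 6 months would give 0.272/exp(−0.0542 × 6) = 38%, but the schedule does not place a typical first test that late.
- **That local and distant failure suffer to the same extent.** As shown above, the effect there is narrower.

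It is also fair that an exponential curve may overstate early death in patients with KPS of at least 70 and adequate organ function.

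**Conclusion.** The point holds for absolute survival in the evaluable-only repeat. Sections 12.2, 12.4 and 10.2.2, read together, give each evaluable patient about 2.5 to 4.5 months of guaranteed survival from registration, with no correction. On the exponential illustration, 2-year survival rises from 27.2% to about 31% to 35% and the median from 12.8 to 15.3 to 17.3 months. Those sizes assume prompt treatment start, the background survival figure and constant hazard; only the upward direction is certain.

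Bias in the hazard ratio remains conditional on differences between arms that the documents do not quantify. The all-patient survival analysis has no immortal time, and the primary endpoint is not touched by this point. It is a modest flaw in a secondary analysis, worth correcting because the correction is nearly free.

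**What to change.** In 12.4, name all randomized patients as the analysis set for overall survival, local failure and distant failure, and limit the evaluable-set repeat to the cognitive and quality-of-life endpoints. State the time origin for local and distant failure.

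If an evaluable-only survival analysis is kept, label it supportive and choose one of two methods, which are not interchangeable:

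- **Delayed entry:** keep registration as the origin, as 10.2.2 requires, and let each patient enter the risk set at the first completed follow-up test.
- **Landmark:** fix one common time in advance and analyze survival after it in patients who are alive and already evaluable at that time.

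Either removes the immortal time. Neither removes selection on having received the assigned treatment, and the text should say so.

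The cost is a few sentences in the plan. No new data and no change in sample size are needed, and the preferred option means fewer analyses.

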3.0 Objectives

3.1 Primary Objectives

- 3.1.1 To assess whether treatment with IMPT results in longer time to cognitive failure compared with IMRT. Cognitive failure is defined as the first cognitive failure on any of the following six cognitive outcome variables: Hopkins Verbal Learning Test Revised (HVLT-R) Total Recall, HVLT-R Delayed Recall, HVLT-R Delayed Recognition, Controlled Oral Word Association (COWA), Trail Making Test (TMT) Part A or Part B.
- 3.2 Secondary Objectives
 - 3.2.1 To determine local control in the brain post radiation treatment.
 - 3.2.2 To determine overall survival in each treatment arm.
 - 3.2.3 To assess quality of life measured at two month intervals for a total of two years post-radiotherapy for both treatment arms.
 - 3.2.4 To assess the pattern of cognitive change in memory at two month intervals for two years post-treatment as well as executive function and processing speed.
 - 3.2.5 MRI diffusion weighted images (DWI) and reconstructed apparent diffusion coefficient (ADC) maps will be analyzed to see if there is a difference between pre- and post-treatment scans. These will also be analyzed for differences between the two treatment modalities.
 - 3.2.6 To evaluate if diffusion tensor imaging (DTI) correlates to the cognitive changes and if there are differences between the two treatment modalities.
 - 3.2.7 To assess the pre-treatment factors of recursive partitioning analysis (RPA) class and mini mental status examination (MMSE) in the predictive determination of local and distant control and cognitive outcome in each treatment arm.
 - 3.2.8 To assess the correlation between location of primary lesion, total volume of intracranial disease, and cognitive outcome in each treatment arm.
 - 3.2.9 To determine the relationship between MGMT promoter methylation status and cognitive and local control outcomes.
 - 3.2.10 To document and descriptively compare post-treatment adverse side effects between the two treatment arms.
 - 3.2.11 To determine the relation between dosimetric parameters and cognitive and local control outcomes.
- 3.3 Correlative objectives
 - 3.3.1 To determine if Apo E (i.e., Apo E2, Apo E3, and Apo E4) genotyping may prove to be a predictor of radiation induced neurocognitive decline (or neuro-protection).
 - 3.3.2 To determine if inflammatory markers (i.e., IL-1, IL-6, and TNF- α) may prove to be predictors of radiation induced neurocognitive decline.

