4.0 Background

Gliomas represent the most common primary brain tumor in the adult population. Malignant gliomas include anaplastic astryocytoma (AA) and glioblastoma multiforme (GBM) and have an annual incidence of 3 to 4 per 100,000, with over 80% of these being GBMs [12]. The standard treatment for glioblastoma is maximal safe resection followed by involved-field radiation. A pooled analysis of six randomized trials demonstrated that there is a significant survival benefit to the addition of radiation therapy after surgical resection [13]. Historically outcomes have been quite poor with median survival of less than one year for GBM [12].

Recently, combined modality treatment including the addition of concurrent and/or adjuvant temozolomide has resulted in significant improvement in outcomes for glioblastoma patients [2, 14]. Stupp et. al. demonstrated a 2 year overall survival (OS) rate of 27.2% with concomitant and adjuvant temozolomide as compared to a 10.9% 2 year OS rate with radiation alone [2]. This response was found to be durable at 5 years of follow up. Indeed, patients with favorable prognostic categories such as MGMT promoter methylation had even better survival outcomes. With improved outcomes and longer survival an increasing number of patients are at risk for secondary adverse effects from radiation treatment, particularly cognitive decline.

Cognitive function has been increasingly recognized as a key primary outcome measurement following cranial radiotherapy. Several studies have suggested that in high grade glioma patients tumor progression was the dominant cause of cognitive decline [15-17]. However, these studies were done in the era prior to the introduction of combined modality treatment when median survival was less than one year. While tumor progression is a key factor in cognitive function, prolonged survival with combined modality treatment will also lead to an increasing number of patients who develop treatment related late toxicity.

Data in low grade glioma patients suggests that the amount of brain exposed to radiation as well as the dose of radiation has a significant impact on cognitive function [3, 4, 18]. Similarly, metastatic brain cancer patients receiving stereotactic radiation have improved cognitive outcomes compared to patients treated with whole brain radiation therapy [19]. This has led to an increased interest in using more focused radiation therapy for glioblastoma.

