- 10.3.6 For analysis of MCP class, all assays will be performed on residual formalin-fixed, paraffin embedded (FFPE) tissue remaining after pathological diagnosis. Representative hemotoxylin and eosin sections will be used to identify tumor content by an M.D. Anderson Neuropathologist. FFPE-derived RNA and DNA will be prepared using the MasterPure Complete DNA and RNA purification kit (Epicentre Biotechnologies, Madison, WI) following deparaffinization using Citrisolve (Amity International, Anderson,SC). *MGMT* promotor methylation and G-CIMP status will be determined by bisulfite conversion of DNA and real-time PCR amplification. *IDH1* status will be determined from the medical record or by direct sequencing when necessary. 19-gene mRNA signature will be determined by real-time PCR following reverse transcription of mRNA

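### MGMT status, prognostic for survival and already to be assayed, is missing from the local-failure, distant-failure and treatment-comparison survival models, and objective 3.2.9 has no analysis

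*Combined protocol and SAP*

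**What the plan says.** The Background (section 4.0) says that "patients with favorable prognostic categories such as MGMT promoter methylation had even better survival outcomes". Section 5.2.4 adds that each molecular component of the MCP, MGMT among them, is prognostic independently of RTOG RPA class. Section 10.3.6 commits to the measurement on residual tissue: MGMT "promotor methylation and G-CIMP status will be determined by bisulfite conversion of DNA and real-time PCR amplification". Secondary objective 3.2.9 is "To determine the relationship between MGMT promoter methylation status and cognitive and local control outcomes"; section 10.2.9 repeats the intent and gives no method.

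Section 7.1 stratifies randomisation by RPA class, MMSE score and age, two levels each. The analysis models in section 12 then contain:

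- Cognitive failure (12.3, Fine-Gray): "Our model will include treatment arm and the stratification factors used at randomization".
- Local failure, and similarly distant failure (12.4, Fine-Gray): "Our model will include treatment arm and the stratification factors used at randomization, as well as selected dosimetric parameters".
- Overall survival (12.4, Cox): arm and stratification factors.
- Quality of life and cognitive test scores (12.4, mixed models): arm, dosimetry, baseline cognition, tumour side and stratification factors.
- Neurocognitive decline (12.4, logistic): ApoE, inflammatory markers, hormones and growth factors.
- MCP class (12.4): distribution by arm, log-rank comparison, and a Cox survival model with arm and stratification factors.

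MGMT appears only in the last of these, as one ingredient of a composite.

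**The concern.** There are two separate gaps.

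First, 3.2.9 asks about MGMT and two kinds of outcome, cognition and local control, and no model in section 12 has MGMT as a term for either. The analysis would have to be devised after the data are in.

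Second, the plan leaves a baseline factor that it regards as prognostic, and will have measured, out of the comparisons where it is most likely to matter. Adjusting for RPA class does not stand in for it, because section 5.2.4 says MGMT adds to RPA class. With 30 to 45 patients per arm, an appreciable chance difference in methylation is not rare. If one occurs, readers will ask whether an apparent difference in survival or local control reflects the radiation modality or the case mix, and the plan has no pre-specified model that answers.

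**Working it through.** **The plan's own figure.** With exponential times, 45% and 30% failure at 4 months give a hazard ratio of ln(0.70)/ln(0.55) = 0.597. Schoenfeld's formula at one-sided 0.20 and 80% power gives 4 × (0.842 + 0.842)² / (ln 0.597)² = 42.5, that is 43 events, as stated in 12.2. Nothing here disputes 43 events or 60/90 patients.

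**Assumed inputs.** The documents give neither MGMT prevalence nor its hazard ratio. I take prevalence 35-45% and a hazard ratio (methylated versus unmethylated) of 0.4-0.6.

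**Chance of imbalance.** With independent binomial counts in two arms of n, a difference of at least 15 points means at least 5 patients at n = 30 and at least 7 at n = 45.

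| Prevalence | 30 per arm | 45 per arm |
|---|---|---|
| 35% | 22.3% | 15.0% |
| 40% | 23.5% | 16.2% |
| 45% | 24.3% | 16.8% |

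These are for either direction. In favour of IMPT alone they halve, to 11-12% and about 8%.

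**Effect on the survival comparison.** Take identical treatments with 15/45 (33%) versus 22/45 (49%) methylated, a difference of 7/45 = 0.156. To first order the unadjusted log hazard ratio shifts by 0.156 × ln(MGMT HR), which gives 0.87, 0.90 and 0.92 for an MGMT HR of 0.4, 0.5 and 0.6. A Cox simulation (exponential survival, assumed median 14 months if unmethylated, uniform censoring at 12-45 months) gives 0.88, 0.90 and 0.93 unadjusted, and 1.00 to 1.01 with MGMT in the model.

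**Error and power.** In a separate simulation (30 per arm, 43 events, prevalence 40%, MGMT acting directly on the outcome with HR 0.5), one-sided error over all randomisations is about 0.20 with or without MGMT. Among trials with at least 10 points more methylation in the IMPT arm, it is 0.31 without MGMT and 0.21 with it. Overall power is 77.7% without and 80.2% with.

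**The primary endpoint, through competing events only.** The cumulative incidence of cognitive failure is λc/(λc+λp) × [1 − exp(−(λc+λp)t)]. The cognitive hazard is λc = −ln(0.55)/4 = 0.149 per month, from the 45% in 12.2. The progression-or-death hazard is λp = ln 2/median, with an assumed median of 5-10 months if unmethylated. MGMT multiplies λp only.

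- Largest effect (median 5, HR 0.4): 35.5% unmethylated versus 40.8% methylated at 4 months. The shift between arms is 5.3 × 7/45 = 0.8 points.
- Smallest effect (median 10, HR 0.6): 39.8% versus 41.8%. The shift is 0.3 points.
- At 24 months the shift is 1.5 to 3.2 points.

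In every case the arm with more methylated patients has the higher cumulative incidence, because fewer of its patients are removed by progression or death first. The design difference is 15 points.

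**The same mechanism bears on 3.2.9.** With median 7 months and HR 0.5, the 24-month cumulative incidence of cognitive failure is about 0.60 unmethylated and 0.75 methylated (0.745 before rounding), although MGMT has no effect on cognition in this calculation. A subdistribution coefficient alone would make methylation look harmful to cognition.

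**The case against.** The strongest reply is that adjusting for stratification factors only is a recognised choice in a phase II screening trial, that randomisation protects the test, and that the gain is modest: about 2.5 points of power in the simulation above. That stands, and it limits the point to precision and interpretation.

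Survival is also partly covered. The MCP Cox model carries arm together with a class that contains MGMT, and class is tabulated by arm. That stands too, but the class merges MGMT with three other markers and RPA class, is presented as validation of the classifier, and does not extend to local or distant failure.

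A reader might infer that an MGMT imbalance could create an apparent proton benefit on the primary endpoint. The documents do not support this. They link MGMT to survival, not to cognition, and through the competing events the shift is under 1 point at 4 months and against the arm with more methylated patients. A reader might also take it as established that local failure depends on MGMT. The documents do not say so; that is part of what 3.2.9 asks, so any size for local failure is conditional.

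Nor is the absence of MGMT from the stratification a fault. It would double 8 strata to 16, or 90/16 = 5.6 patients per stratum against a block size of 6, and no section says the result is available before randomisation.

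**Conclusion.** The point holds for the secondary comparisons and for objective 3.2.9. The missing analysis for 3.2.9 follows from the text and needs no assumption. The adjustment argument rests on assumed prevalence and hazard ratios. Within the ranges used, an imbalance of 15 points or more has a probability of 15-24%, and one of that order can move a null survival hazard ratio to about 0.88-0.93. If MGMT has little effect on an outcome, little changes for that outcome. The validity of the test, the sample size and the primary cognitive-failure model are not in question. This should be corrected before analysis, but it does not threaten the trial.

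**What to change.** In 12.4, keep the stated models and pre-specify companions:

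- Add baseline MGMT status to the Fine-Gray models for local and distant failure and to the Cox model for overall survival.
- Leave the primary model in 12.3 unchanged and add an MGMT-adjusted sensitivity model for cognitive failure.
- Define the variable in advance: either the three MGMT groups implied in 5.2.4 or a stated binary cut, with a level for status not available.
- For 3.2.9, report the MGMT coefficient from the local-failure model. For cognitive failure, report both the cause-specific and the subdistribution hazard ratios, so that an effect on progression is not read as an effect on cognition.
- Do not add MGMT to the stratification.

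The cost is wording, since the assay is already planned. In the cognitive sensitivity model, a binary status plus a not-available level takes the parameters from 4 to 6, and events per parameter from 43/4 = 10.8 to 43/6 = 7.2. Using three groups plus not available gives 43/7 = 6.1, which favours the binary cut there. Some patients will have no residual tissue and will fall in the not-available level.
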